1 PROJECT SUMMARY

TITLE	Conservative management of triangular fibrocartilage injuries
INVESTIGATORS	
Primary: [name] (Principal Investigator), [name], [name], [name], [name]
 
Associate: [name], [name], [name]

OBJECTIVES	
Primary Objective: To determine the efficacy of splint immobilisation and cortisone injection, used in isolation or combination, for the non-operative management of triangular fibrocartilage complex injury.
 
Secondary Objective: To determine the prevalence and factors associated with TFCC tears not benefitting from a course of conservative treatment.

STUDY DESIGN	Randomised control trial
SITES	Brisbane Private Hospital, Brisbane, Australia
NUMBER OF SUBJECTS	180 participants (45 per treatment group) will be recruited in this study
TARGET POPULATION	Adults presenting with clinical and MRI confirmation of isolated TFCC tear, no greater than 12 months from primary injury.
LENGTH OF CLINICAL INVESTIGATION	
It is anticipated that this study will require 50 months from commencement of recruitment (24-month recruitment period) to final data collection and analysis. Study participants will be assessed at baseline (pre-intervention) and post intervention intervals.
 
The primary end point of the study will be 12 weeks post initiation of conservative treatment to determine treatment effectiveness.
 
The secondary end point of the study will be at 24 months to monitor long term outcomes and ascertain rates of re-injury or recurrence of symptoms.

OUTCOMES	
Primary Outcomes:
 
 ▪ Pain and function using Patient Rated Wrist and Hand Evaluation (PRWHE) 
Secondary Outcomes:
 
 ▪ Improvement in symptoms and function using the global rating of change 15-point scale (GRC) ▪ Disability using the abbreviated version of the Disabilities of the Arm, Shoulder and Hand Score (QuickDASH) ▪ Pain and satisfaction using a visual analogue scale (VAS) ▪ Health-related quality of life using the EQ-5D-5L ▪ Grip strength measured using a hydraulic dynamometer ▪ Complications or adverse events

2 INTRODUCTION

Injury to the triangular fibrocartilage complex (TFCC) is recognised as a common cause of both short and long-term wrist pain and loss of wrist function, with a resultant impact on quality of life. At present, it is common practice in Australia and overseas for health care providers to initially recommend non-operative or 'conservative' treatments for patients. Studies of conservative management are limited despite being the first line of treatment for TFCC injury, with failure of non-operative management an indication for surgical treatment.

This study will investigate the efficacy of non-operative treatments in relieving symptoms and improving function in adults with TFCC tears. It will be conducted as a four-arm randomised trial which will compare routinely used combinations of non-operative interventions. Hand therapy used in isolation will be compared to therapy with splint immobilisation, therapy with corticosteroid injection and a combination of the three treatments, for TFCC injury management. It is expected that the outcome of this study will have a substantial contribution to the evidence-base for the initial, non-operative management of TFCC injuries in standard practice worldwide.

2.1 LITERATURE REVIEW

Located at the distal radioulnar joint (DRUJ), the triangular fibrocartilage complex (TFCC) is an intricate anatomical structure which plays a significant role in wrist biomechanics. The TFCC is comprised of an articular disc of triangular fibrocartilage, meniscal homologue, the ulnar collateral ligament (UCL), volar/palmar and dorsal radioulnar ligaments, ulnolunate and ulnotriquetral carpal ligaments and extensor carpi ulnaris (ECU) subsheath. The cartilaginous ligament complex is recognised as a major stabiliser of the DRUJ and carries approximately 20% of the axial load of the wrist (Palmer, Glisson, & Werner, 1984; Palmer & Werner, 1981). In forearm pro-supination, the TFCC acts to inhibit dorsal displacement and when loading in extension, helps to distribute the load between the ulna and radius. Despite its role in protective wrist function in high stress conditions, the TFCC itself remains vulnerable to injury under torsional force and repetitious loading.

As per the Palmer Classification System (1989), injury to the TFCC is most often described in two major categories: Type 1 acute traumatic injury or Type 2 chronic degenerative conditions. This injury classification system further branches into subgroups A to D in Type 1 injury to indicate location of injury or involved structures, and A to E in Type 2, which sequentially increases with condition severity. Palmer classification of injury severity, with consideration to blood supply to the affected region, is often utilised to justify the suitability of surgical procedures for cases published in literature.

Vasculature of the TFCC is characterised by a well-supplied peripheral margin arising ulnarly from the dorsal and volar attachments, with a central avascular region (Bednar, Arnoczky, & Weiland, 1991). Type 1A central tears to the articular disc are thought to have a low potential for healing with surgical repair, due to poor vascularisation of the inner region (Atzei, Rizzo, Luchetti, & Fairplay, 2008; Rein et al., 2015). Type 1 B and C tears are situated at the well-vascularised periphery and thus are often repaired surgically if non-operative management in the acute period is unsuccessful. Despite Type 1D tears having varying degrees of blood supply due to the involvement of the avascular radial attachment, the peripheral blood supply often lends itself to operative treatment approaches also. In contrast, there is little research available relative to TFCC microvasculature and its relation to suitability of non-operative interventions. Even more so, literature is lacking concerning implications of vascularity to injury progression in the absence of intervention.

Degenerative TFCC injuries are influenced by age, gender, repetitious loading and positive ulnar variance (UV) of the DRUJ. Chronic TFCC lesions are a recurrent finding in cohorts of collegiate, elite or professional athletes who participate in sports which involve repetitively exerting force in wrist hyperextension, pronation or deviation. Chronic ulnar-sided wrist pain, with crepitus or instability is often reported by gymnasts, basketball, golf and tennis players, particularly those with positive UV (Jarrett & Baratz, 2012; Ko & Wiedrich, 2012; Pang & Yao, 2017). Ulnar impaction is recognised as a primary contributor to central TFCC tears with absent damage to peripheral, dorsal and ulnar structures. The length of the ulnar, when compared to radial length at the DRUJ, has been found to have an inverse relationship with thinning of the TFCC, observable on MRI between the ulnar and lunate (Palmer et al., 1984; Roenbeck & Imbriglia, 2011). Yoshioka found a near linear decrease in TFCC thickness on MRI with increase in UV >1mm, with an average 1.56mm ulna positive variation in patients with substantial TFCC disruption in comparison to 0.05mm in asymptomatic volunteers (Yoshioka et al., 2007).

Initial treatment for clinically indicated and MRI confirmed TFCC tears typically begins with 4 weeks of splint or cast immobilisation with or without intra-articular corticosteroid injection, though this approach lacks a solid evidence base despite its routine prescription. Park (2010) reported that 57% of patients with clinically suspected (but radiologically unconfirmed) TFCC injury had complete resolution of symptoms after a 4-week course of wrist immobilisation, irrespective of splint or cast type used (Park, Jagadish, & Yao, 2010). Lee (2019) found that 15% of patients in their retrospective review progressed to surgical interventions following a course of extended splint wear (4-12 weeks) and 37% experienced worsening or no change in PRWHE scores (Lee, Hwang, Lee, & Kwon, 2019). Two case-studies have found benefits using prolonged non-operative management; one using a neoprene orthosis for 12 weeks after 4 weeks of

immobilisation and corticosteroid injection, and the other a 12-week sensorimotor therapy protocol 2 months initial post injury (Barlow, 2016; Chen, 2018). Both case studies found significant improvement in pain and function following the 3 months of extended non-operative management. In studies investigating other hand and wrist conditions, research has supported trials of early mobilisation and heat wrapping for short-term functional benefits, though evidence is lacking to demonstrate any potential long-term benefits (Michlovitz, Hun, Erasala, Hengehold, & Weingand, 2004; Roll & Hardison, 2017). A 13-15 year follow up on untreated, arthroscopically confirmed TFC tears associated with distal radius fractures found that the presence of TFCC abnormality did not significantly impact long-term recovery outcomes (Mrkonjic, Geijer, Lindau, & Tagil, 2012). There are noticeably fewer publications specific to non-operative interventions in comparison to those investigating surgical procedures and an even larger gap in the literature regarding the natural progression of untreated TFCC pathology.

The benefits of a prolonged period of non-operative management for recalcitrant ulnar-sided wrist pain is inconclusive. This randomised control trial will investigate routinely used non-operative interventions, hand therapy, splinting and corticosteroid injection, to determine their efficacy in resolving symptoms. The outcomes of this trial will help determine whether splinting or cortisone injections, in isolation or combination, provide any additional benefit compared to hand therapy alone for non-operative treatment. This will contribute to the literature regarding non-operative interventions for TFCC injury management, and may also offer a greater understanding of TFCC injury pathology in the absence of any treatment. It is our aim to develop an evidence-based treatment protocol for managing TFCC tears non-operatively, with the potential to increase rates of successful conservative intervention.

3 PURPOSE OF THE INVESTIGATION

The purpose of this investigation is to determine the clinical outcomes and efficacy of the various conservative treatments offered to patients who suffer from triangular fibrocartilage complex tears.

3.1 RESEARCH QUESTION

Do adults with acute tears to the triangular fibrocartilage complex receiving a combination of the hand therapy, thermoplastic splint immobilisation and a corticosteroid injection to the TFCC (Group D) have significantly greater improvement in pain and function, as compared to those receiving just one conservative treatment of either splinting (Group B), or corticosteroid injection (Group C), or the control treatment of hand therapy (Group A)?

3.2 OBJECTIVES

3.2.1 Primary Objective

To determine the efficacy of splint immobilisation and cortisone injection, used in isolation or combination, for the non-operative management of triangular fibrocartilage complex injury.

3.2.2 Secondary Objectives

To determine the prevalence and factors associated with triangular fibrocartilage complex tears not benefitting from a course of conservative treatment.

3.3 NULL HYPOTHESIS

Patients receiving a combination of hand therapy, splint immobilisation, and corticosteroid injection (Group D) will have no greater improvement in pain and function, compared to those receiving the splint immobilisation (Group B), or corticosteroid injection (Group C), or the active control treatment of hand therapy (Group A) in adults with triangular fibrocartilage complex tears. In testing the main effects, the null hypothesis is that the means of all groups for the corresponding effect are not significantly different.

4.2 INVESTIGATOR RESPONSIBILITIES

The Primary Investigators will be responsible for:

- Monitoring the conduct of the study and study processes in line with the study protocol;
- To report any adverse events to the ethical committee, and relevant persons.

All Investigators will be responsible for:

- Obtaining ethical clearance prior to the commencement of the study;
- Recruitment;
- Providing participants with informed consent prior to allocation of intervention;
- Random allocation of participants;
- Provision of intervention;
- Concise and comprehensive collection of clinical and radiological data from the participants (blinded for collection of clinical outcomes);
- Ensuring confidentiality of data collection forms and results;
- Ensuring data is kept in a safe, secure and lockable location, and electronic copies have been backed up on a secure server;
- Ensuring the study is conducted in a safe and ethical manner in line with Queensland Health policies and procedures, NHMRC guidelines and relevant laws;
- Maintaining the confidentiality of participant records and data collected, and abiding by the NHMRC guidelines for human research;
- Data input from paper into electronic format;
- Data analysis;
- Paper preparation and submission; and
- Adherence to the Good Clinical Practice Guidelines.

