8.2 RANDOMISATION

Block randomisation will be performed to achieve balance in the allocation of participants to the different treatment arms throughout the course of the recruitment period. Fifteen blocks will be generated, with three multiples of each treatment arm per block. As a result, for every 12 randomly assigned treatment allocations, each intervention arm will have a comparable number of participants.

The randomisation sequence will be concealed in sequentially numbered sealed, opaque envelopes. The randomisation procedure will be administered by a research assistant who will not be blind to allocation for the duration of the study. They will open an envelope and reveal the allocation to the patient. As all treatment groups involve a hand therapy session, all participants will be provided with a referral for hand therapy by their referring surgeon when enrolled in the study. A dual randomisation procedure will be implemented, with one envelope opened at baseline and the other at the 6 week interval. At the baseline appointment, the assessor will open an envelope to reveal whether the participant will be receiving a splint.

A second randomisation will occur at 6 weeks to reveal whether the participant is to have a cortisone injection. Each envelope will contain a sheet of paper with the intervention group, as listed below.

Group A Hand Therapy (HT)	Group B HT + Splint	Group C HT + Cortisone	Group D HT + Splint + Cortisone
-------------------------------------	-------------------------------	----------------------------------	---

If randomly allocated into Group C or Group D, the participant's study surgeon will issue a referral for a cortisone injection to be administered at Brisbane Private Imaging, 6 weeks after the baseline appointment. The treating surgeon will not be blind to allocation to maintain standard medical care.

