8.3.3 Patient-Reported Questionnaires

Participants will complete a digital questionnaire at assessment intervals with the help of a research assistant, to record changes to wrist pain and function (Appendix 14.4). The patient-reported surveys comprise the primary and secondary outcome measures specified in section 7, *Study Outcomes*. These questionnaires will be completed by participants at baseline prior to randomisation and at 6 weeks, 12 weeks, and long-term follow-up intervals.

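### Outcome collection is called blinded, but the protocol has the assessor open the allocation envelope and nowhere separates outcome assessment from randomisation

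*Protocol*

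**What the plan says.** Section 4.2 lists duties shared by all investigators. One is "Concise and comprehensive collection of clinical and radiological data from the participants (blinded for collection of clinical outcomes" (the closing bracket follows in the source). The same list includes "Random allocation of participants" and delivering the treatments.

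Section 8.2 describes allocation:

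- "The randomisation procedure will be administered by a research assistant who will not be blind to allocation for the duration of the study".
- Participants are told their allocation by this assistant.
- "At the baseline appointment, the assessor will open an envelope to reveal whether the participant will be receiving a splint". A second envelope, for the injection, is opened at 6 weeks.
- "The treating surgeon will not be blind to allocation to maintain standard medical care".

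Section 8.3.3 covers the questionnaires, which include the primary PRWHE: "Participants will complete a digital questionnaire at assessment intervals with the help of a research assistant". Section 8.3.4 has a research assistant measure wrist motion, grip and pinch. Section 8.5.1 has a research assistant measure outcomes at the 12-week primary end-point, with the referring surgeon also assessing the participant. None of 8.3.3, 8.3.4 or 8.5.1 says whether that assistant is blinded, or whether it is the person who randomised.

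Sections 8.4.2 and 8.4.4 collect splint-wear compliance at the follow-up research assessments. Section 7.2.6 has splint and injection reactions checked at each assessment.

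**The concern.** Blinded outcome collection is a stated property of the trial and would normally be carried into the report. The only sentence in 8.2 that mentions an assessor has that person learn the splint allocation. If the same person measures outcomes later, the stated blinding is not delivered.

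This matters most for grip and pinch strength, where encouragement from staff can influence effort, and for goniometer readings, which staff take by hand. For the PRWHE there is a separate difficulty. Participants rate themselves and know their treatment, so blinding the data collector cannot make that outcome blinded. A reader who took 4.2 at its word would credit the primary result with a protection it cannot have.

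**Working it through.** The protocol gives no figure on this point, so the check is a comparison of the text.

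**Step 1: who is the assessor in 8.2?** There are three readings.

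1. The assessor is the randomising research assistant under another name. That person is unblinded throughout by 8.2's own statement, so outcomes collected by them are not blinded.
2. The assessor is a different person who collects outcomes. By opening the baseline envelope, that person learns the splint allocation.
3. The word is a slip, and the envelope is opened by an assistant who collects no outcomes. This fits 4.2, but the text does not say it.

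Readings 1 and 2 contradict 4.2. Reading 3 needs 8.2 to be corrected.

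**Step 2: is a blinded assessor provided elsewhere?** Sections 8.3.3, 8.3.4 and 8.5.1 refer only to a research assistant, and the visit table in 8.5.1 to a researcher. None of them gives a way to keep that person unaware of allocation. The part of section 4 just before 4.2 was not available for this review, so this step covers only the remaining text.

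**Step 3: would someone who never opened an envelope stay blind?** Not reliably. The research assessments include splint compliance (8.4.2, 8.4.4) and splint or injection reactions (7.2.6). Anyone who asks about these before measuring can learn the treatment, and no order within the visit is set.

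**Step 4: which data are exposed?**

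| Assessment | Exposure |
|---|---|
| Baseline | None: 8.1.2 and 8.3.3 place data collection before randomisation |
| 2 weeks | Compliance and complications under 8.5.1, no PRWHE; 8.3.4 has motion recorded at all intervals, so motion here is unclear |
| 6 weeks | PRWHE, strength and motion; splint allocation already known to whoever opened the first envelope; order relative to the second envelope not stated |
| 12 weeks (primary) | PRWHE, strength and motion in person, after both envelopes |
| 6, 12 and 24 months | Exposed if in person; 8.5.2 also allows an emailed survey with questionnaires only |

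**Step 5: which outcomes can be blinded at all?** Under 8.2 the participant is told the allocation, so every patient-reported score is unblinded at source. Assessor blinding can protect only the staff-measured outcomes and any staff influence on how the questionnaires are completed.

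**The case against.** The best defence is that 8.2 singles out one assistant as unblinded, which makes most sense if other staff are blinded. Section 8.1.2 refers to research assistants in the plural. On that view a second, blinded assistant collects outcomes and the word assessor is a drafting slip. This is possible and the text does not exclude it. But a blinding claim needs a stated provision, and the wording in 8.2 points the other way.

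A reader might infer several stronger things that the protocol does not support:

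- *That the unblinded randomising assistant helps participants with the PRWHE.* Section 8.3.3 does not identify the helper, and the help may be purely technical. What stands is that the helper's blinding is not stated.
- *That opening the envelope at the baseline appointment compromises the baseline data.* Those data are complete before randomisation.
- *That every in-person visit is affected.* Step 4 shows otherwise.
- *That assisted completion shifts the PRWHE by some number of points, to be set against the 14-point clinically important change.* Nothing in the protocol supports a figure. A treatment comparison would also be biased only if the shift differed between arms.
- *That assessor blinding would remove bias from the primary outcome.* It would not, because participants know their treatment.

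It is also fair that motion is not listed among the outcomes in section 7 and that strength is secondary. This limits the consequences but does not remove the contradiction.

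**Conclusion.** The point holds in a limited form. Section 4.2 states blinding that the written procedure in 8.2 does not deliver, and the research assessments contain further routes to unblinding. The exposure lies in the in-person outcome visits after randomisation, chiefly week 12, and mainly in grip, pinch and motion. The PRWHE cannot be called blinded under any staffing arrangement; staff help with it is an added, avoidable risk.

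The size of any bias cannot be estimated from the protocol, and the sample size calculation is unaffected. The conclusion assumes that the unavailable part of section 4 does not name a separate blinded assessor. If it does, 8.2 still needs correcting and the order of the visit still needs to be set. The matter should be corrected; it does not undermine the design.

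**What to change.** 1. In 8.2, replace 'the assessor' with 'the unblinded research assistant'.
2. In 8.3.3, have participants complete the PRWHE and the other questionnaires alone on the device, before contact with staff at the visit and, at 6 weeks, before the second envelope is opened. Limit help to technical problems.
3. In 8.3.4 and 8.5.1, have strength and motion measured by an existing assistant who opens no envelopes, before any compliance or adverse-event questions. Those questions go to the unblinded assistant. At 6 weeks, take these measurements before the second envelope too. Ask participants not to mention their treatment to the measuring assistant.
4. If existing staff cannot split these roles, delete the blinding claim in 4.2.
5. In either case, state that participants and treating surgeons are unblinded and that the primary outcome is an unblinded self-report.

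The cost is wording, a fixed visit order and possibly slightly more missing questionnaire items without assistance. Section 11.1 describes staff time as in kind, with research assistant time forming part of a degree, and the number of assistants is not given. Whether item 3 is feasible is therefore for the sponsor to confirm. Items 1, 2, 4 and 5 need no extra staff.

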5 STUDY DESIGN

This study aims to determine if there are differences in the effectiveness and clinical outcomes of various conservative treatments offered to patients who suffer from triangular fibrocartilage complex (TFCC) tears. A four-arm (Section 2.4) factorial, randomised clinical trial will be implemented.

Participants will be randomly allocated to either an active control group or one of three intervention groups. Participants will be asked to complete an electronic questionnaire consisting of outcome measures designed for conditions specific to the hand and wrist. Outcome measures will be administered at baseline (pre-treatment); 6 and 12 weeks (primary end-point); and at 6, 12 and 24 months from baseline (secondary end-point). Compliance and complications will be recorded at all post-intervention intervals, including two weeks after treatment commencement.

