7 STUDY OUTCOMES

Patient-reported pain and function questionnaires will be administered at baseline, 6 and 12 weeks; and 6, 12 and 24 months post baseline. Compliance and adverse events will be recorded at all post-intervention intervals, including 2 weeks after treatment initiation.

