8.4.1 Hand Therapy

It was deemed unethical to the investigators to have a control group where participants did not receive any treatment at all, as all participants will be patients referred to the surgeons seeking relief of their symptoms.

For this reason, all participants irrespective of the group they are allocated to, will receive hand therapy. The active control group (Group A) will receive only the hand therapy. Hand therapy with a qualified hand therapist will be provided by Extend Rehabilitation (www.extendrehab.com.au) or EKCO Hand Therapy (www.ekco.com.au) at Brisbane Private Hospital. The baseline treatment appointment and the follow-up sessions for all participants at 2- and 6-weeks post intervention will be provided at a subsidised cost of \$180 for the three sessions. The normal cost for patients outside of the research would be \$360 for these three sessions (Appendix 14.5).

Participants will receive a standardised exercise program and advice on pain management including joint protection and activity modification. This therapy protocol will be reinforced with the provision of a participant exercise booklet, vinyl dumbbells and a compliance log (Appendix

14.6). Therapists will undergo a regular in-service training program to ensure that all participants receive standardised treatment.

Routine follow-up appointments will be provided at 2, 6- and 12-weeks post-intervention. Participants having any concerns or queries between clinical visits will have the contact details for the research institute as first point of contact. The research team will advise their consulting surgeon's practice or treating hand therapist clinic so that appropriate advice can be provided. Any deviation from the prescribed treatment protocol will be recorded at follow up research assessments.

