8.4.3 Corticosteroid Injection

A single dose of ultrasound guided intra-articular corticosteroid injection will be provided by radiologists at Brisbane Private Imaging (Brisbane Private Hospital, Brisbane) at the 6 week interval. The steroid (Celestone Chronodose™) and local anaesthetic (Marcain™) combination to be administered, is the current hydrocortisone & local anaesthetic (HCLA) medication routinely used at Brisbane Private Imaging. A standard procedure will be followed:

1. Participant will be asked to lie in a supine position on the examination table with the affected wrist resting comfortably palm side down on the table or across their abdomen.
2. Antiseptic solution will be applied to the skin.
3. A 25 gauge, 38mm needle will be inserted into the dorsal aspect of the TFCC using ultrasound guidance.
4. A mixture of 1 mL of Celestone Chronodose and 1 mL of 0.5% Marcain will be injected into the TFCC.

The injections will be provided by radiologists at Brisbane Private Imaging, at the Brisbane Private Hospital. The treatment will be bulk billed for the participants (Appendix 14.7)

Celestone Chronodose™ (Merck Sharp & Dohme Pty Ltd, Australia) contains 1ml of betamethasone 5.7mg. It has full TGA approval (Appendix 14.8).

Marcaïn™ (AstraZeneca PTY Ltd, Australia) contains the active ingredient bupivacaine hydrochloride monohydrate. It has full TGA approval (14.9).

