8.5.1 Primary End-point

Participants will be assessed by their referring surgeon and have outcomes measured by a research assistant at 12 weeks to assess effectiveness of the randomised conservative treatment for treating the injury. Patients who demonstrate no benefit from conservative management, or an aggravation in symptoms may be considered for further conservative treatment or surgical intervention at the surgeon's discretion. Any further treatment received will result in the conclusion of the participant's ongoing study involvement. Assessments will be made at 2 and 6 weeks to monitor compliance to the treatment allocated, complications/adverse events and an interim assessment of treatment outcomes (6 weeks only).

Data Collection Interval	Range	Review Method
Pre-intervention/baseline	≤ 12 months post initial injury	In person at the clinic Surgeon + Researcher + Hand Therapist
2 weeks Compliance & complications	2 weeks +/- 5 days	In person at the clinic Researcher + Hand Therapist
6 weeks Interim Assessment	6 weeks +/- 10 days	In person at the clinic Researcher + Hand Therapist + Surgeon

12 weeks Primary End-Point	2 – 4 months	In person at the clinic Surgeon + Researcher
-------------------------------	--------------	---

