9.3 DATA ANALYSIS

Baseline demographic and clinical data will be reported using descriptive statistics and will be tabulated. Between groups differences in baseline data will be examined using unpaired conventional tests of hypothesis depending on the nature of the data. Between group and within group differences in outcome measures over time will be examined using a priori unpaired and paired conventional tests of hypothesis depending on the nature of the data. Linear mixed effects models will be used to examine the within and between group variability of the four groups. Bonferroni adjustments for multiple comparisons will be made where appropriate to mitigate risk of type-1 error.

The complication rates will be reported in terms of frequency. The frequencies of complications will be compared using statistical analysis such as the Pearson chi-square statistic.

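### The early complication check comes about four weeks before the injection, so the first scheduled check after injection is the 12-week visit and short-lived injection reactions may be missed

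*Protocol*

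**What the plan says.** Section 5 sets the timing of safety recording: "Compliance and complications will be recorded at all post-intervention intervals, including two weeks after treatment commencement". Section 7 repeats it: "Compliance and adverse events will be recorded at all post-intervention intervals, including 2 weeks after treatment initiation". Section 8.5.1 gives the purpose of the early visits: "Assessments will be made at 2 and 6 weeks to monitor compliance to the treatment allocated, complications/adverse events". Its table lists four intervals: baseline, 2 weeks (±5 days), 6 weeks (±10 days) and 12 weeks (range 2–4 months). Nothing is listed between the 6-week and 12-week visits.

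The treatments do not all start together. Section 8.4.1 describes hand therapy as "The baseline treatment appointment and the follow-up sessions for all participants at 2- and 6-weeks post intervention", and section 8.4.2 has the splint fitted after the baseline therapy session and worn full time for 6 weeks. The injection comes later. Section 8.2 says: "A second randomisation will occur at 6 weeks to reveal whether the participant is to have a cortisone injection", and has the surgeon refer participants in Groups C and D for a "cortisone injection to be administered at Brisbane Private Imaging, 6 weeks after the baseline appointment". Section 8.4.3 also gives the 6-week interval.

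Section 7.2.6 puts injection reactions first in its list of possible adverse events, undertakes to monitor events closely, and says they are checked at each assessment. Section 9.3 adds: "The frequencies of complications will be compared using statistical analysis such as the Pearson chi-square statistic".

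**The concern.** The two early checks suit treatments that begin at baseline. They catch splint and exercise reactions while those treatments are in use. For the injection, week 2 falls well before the exposure and week 6 is when it is assigned, so neither is a post-intervention check for that treatment.

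Section 6.2 names infection, bruising, bleeding and drug reaction as injection risks. Some of these may come and go within days or a few weeks. If nobody asks until the 12-week visit, a mild or resolved reaction enters the data only if the participant remembers it or reported it unprompted. Splint reactions occur only in Groups B and D, and injection reactions only in Groups C and D. A difference in how closely the two kinds of reaction are sought can therefore carry over into the comparison of complication frequencies between arms. At stake are the safety description of one of the two treatments under test and its early detection of harm.

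**Working it through.** **Inputs (protocol).** Early check: 2 weeks ±5 days (8.5.1), counted from treatment start (5, 7). Treatment start: baseline therapy session (8.4.1, 8.4.2), taken here as day 0. Injection: 6 weeks after baseline (8.2, 8.4.3). 6-week visit: ±10 days. 12-week visit: 2–4 months. Group size: 45 in each of four groups (9.1). One month is taken as 30.44 days. The protocol states no figure of its own for the interval from injection to first check, so there is none to reproduce.

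**Week-2 check relative to injection**
- Nominal: 42 − 14 = 28 days before injection.
- Window of the check: 14 − 5 = day 9 to 14 + 5 = day 19.
- If the injection moves with the 6-week visit (day 32 to 52): 32 − 19 = 13 days to 52 − 9 = 43 days before. The check precedes the injection in every case.

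**First scheduled check after injection**
- Nominal: 84 − 42 = 42 days.
- 12-week window: 2 × 30.44 = day 61 to 4 × 30.44 = day 122.
- Injection fixed at day 42: 61 − 42 = 19 days to 122 − 42 = 80 days.
- Injection assumed to move with the 6-week visit window: 61 − 52 = 9 days to 122 − 32 = 90 days. This pairs opposite extremes, and the protocol gives no window for the injection itself.

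**Scheduled checks after the start of each treatment**

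| | Splint | Injection |
|---|---|---|
| By week 12 | 3 (weeks 2, 6, 12) | 1 (week 12) |
| To 24 months | 6 (adding months 6, 12, 24) | 4 (week 12; months 6, 12, 24) |

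The count matters less than the placement: two splint checks fall within the six weeks of full-time wear, while no injection check is scheduled in the nominal six weeks after the dose.

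**Participants affected.** Groups C and D: 45 + 45 = 90 planned.

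**What cannot be computed.** The protocol gives neither a reaction rate nor a capture rate. Purely as an illustration with assumed values, recorded events = 90 × true rate × share captured:

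| Assumed true rate | 100% captured | 75% | 50% | 25% |
|---|---|---|---|---|
| 5% | 4.5 | 3.4 | 2.3 | 1.1 |
| 10% | 9.0 | 6.8 | 4.5 | 2.3 |
| 20% | 18.0 | 13.5 | 9.0 | 4.5 |

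These show how loss would scale. They are not estimates for this trial.

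**The case against.** A reader might infer that the complication comparison does under-count injection reactions and is biased in favour of the injection. The documents do not support that. All four arms are asked at the same times. Section 7.2.6 has injection reactions checked at every assessment, so the 12-week form does ask about them. Section 8.4.1 gives participants a contact point between visits, with onward referral to the surgeon's practice or the therapist. Complications also include wrist instability and reinjury, which can occur in any arm. Section 6.2 regards the listed drug reactions as very uncommon, so few events may be involved. Group D receives both treatments, so 3 checks against 1 is a contrast between treatments and not between arms. These points stand, and they limit the claim to a risk of unknown size.

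They do not remove it. A common schedule does not give equal capture when the reactions are specific to treatments that start six weeks apart. The between-visit route relies on the participant to make contact, and the promise of close monitoring comes with no added contact.

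Section 8.4.1 also mentions follow-up at 2, 6 and 12 weeks after intervention, which might be read as counting from the injection. The same section gives the therapy sessions for all participants as baseline, 2 and 6 weeks, and the table in 8.5.1 has a single set of rows starting at baseline, so that reading fails.

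**Conclusion.** The timing point holds. On the protocol's schedule, no complication check is planned between the injection and the 12-week visit, a nominal gap of 42 days. The range is about 19 to 80 days with the injection on day 42, and about 9 to 90 days only on the added assumption that it shifts with the 6-week visit window. Both rest on treatment starting at or close to baseline.

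The consequence is a risk that short-lived injection reactions in 90 planned participants are under-ascertained relative to splint reactions. Actual under-counting or bias is not shown, and its size cannot be derived from the protocol. Complications are a secondary outcome and the primary analysis is unaffected. This is an inexpensive improvement to safety data, and it belongs in the protocol because an analysis plan cannot recover information that no contact collects.

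A related inconsistency needs attention. Section 8.4 has radiology appointments made, where needed, after allocation at the baseline visit, whereas section 8.2 reveals injection allocation only at 6 weeks. This does not alter the timing above, since 8.2 and 8.4.3 agree on an injection at 6 weeks.

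**What to change.** Add one row to the table in section 8.5.1: a short remote complication and compliance form, by email or phone, about two weeks after the 6-week visit (week 8), using the existing adverse-event form. Send it to all four arms, so that any extra reporting it prompts does not fall on the injected groups alone. Amend sections 5 and 7 so that the recording times include this contact. Any breakdown of complications by period can be left to the SAP.

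Reconcile sections 8.2 and 8.4 on when injection allocation becomes known and when radiology appointments are made.

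The cost is up to 180 brief forms and a protocol amendment, with no added visit or procedure. The downside is one extra short contact per participant.
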